## Study setting

In Korea, the national fire department exclusively operates the EMS system, and EMS CPR protocol follows the 2010 and 2015 American Heart Association (AHA) guidelines. Ambulance crews can provide CPR at the scene and during transport, but they cannot stop CPR in the field unless the return of spontaneous circulation (ROSC) occurs and cannot declare death in the field because only a physician can declare death. Seoul is a large metropolitan city with a single-tiered intermediate level EMS. The population of Seoul is approximately 10 million in an area of 605 km^2. One dispatch center is responsible for the entire city, and a DA-CPR protocol was adopted in late 2010. Seoul is composed of 25 administrative and health districts. Each district consists of a number of neighborhoods ('town level'). There are an average of 17 neighborhoods in each district (total 429 neighborhoods). Average population of districts is approximately 400,000 in an average area of 24 km^2 and the average population of the neighborhoods is 20,000 in an average area of 1.5 km^2.

## Intervention program

In May 2015, Seoul launched the TM alert system, called the dispatch-activated neighborhood access defibrillation and cardiopulmonary resuscitation program ("NAD-CPR" program) in 5 districts serving a population of 2.2 million (Gangdong-gu, Gangbuk-gu, Nowon-gu, Seocho-gu, and Jungnang-gu). The intervention consisted of three major components: registration of volunteers after CPR training, active installation and registration of a PAD, and dispatcher activation of registered volunteers for bystander CPR and defibrillation.

First, the CPR volunteer network was organized for those who agreed to register for the TM alert system after completing the CPR training courses provided in participating district health center. The CPR network was explained to the all trainee when CPR training was conducted and the trainees voluntarily registered themselves to the network after training. They were trained with a 1-hour CPR training course and received a certification card from the city mayor. The volunteers' telephone number, workplace address, and home address were collected and transferred to the dispatch center to integrate with the EMS call system. For quality control of the CPR trainee, the volunteer registration remained valid for 2 years, and after that it was automatically removed. If someone want to remain in the network after two years, they should be attend CPR renewal course and register again. The program started in

2013 as a pilot program and was implemented in 2014.

Second, the Seoul health authority expanded the installation of PADs. All PADs were registered in the National Emergency Medical Center by the EMS Act, and the PAD registry was developed and recorded for use. The active installation and registration of the PADs were guided by each district's health authorities at predesignated places by the EMS Act, such as public and commercial buildings, traffic stations, sports and cultural areas, and large-sized apartments. The city government provided half of the financial support for PADs, and the remainder were deployed by the private sector.

Third, according to the DA-CPR protocol, the dispatcher asked two key questions regarding altered mental status and abnormal breathing. When a suspected arrest occurred, to issue an alert about an OHCA event, the dispatchers pushed a button to send a short text message containing the location of the cardiac arrest and the location of nearest available PAD to registered all volunteers within one geographic town according to a time window. This time window address-matched volunteers to their workplace or home address during the intervals from 6 AM to 22PM. The protocol for the TM alert service was not applied to all OHCA, especially in cases which occurred during the time interval from 00:00-05:59 and 22:00-23:59, because the night was regarded as an ineffective time to alert volunteers due to being too late.

The dispatchers, EMS crew, registered CPR volunteers, and medical record reviewers who were employed to review the hospital outcomes by the Korea CDC were blinded to the study intervention.

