### Study design

This was a non-randomized, pre- and post-intervention trial. Since the intervention program started in May 2015, the period from January 2013 to December 2014 was defined as the pre-intervention period, and the period from January 2015 to December 2016 was defined as the post-intervention period. The TM cases were defined as the cases for which an TM alert was sent. Other cases were defined as standard care cases (non-TM cases).

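### The 2013–2014 reference period is partly exposed to the volunteer component, so the before/after odds ratio does not estimate the full three-component programme against no programme

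*Combined protocol and SAP*

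**What the plan says.** The Intervention program section sets out a package: "The intervention consisted of three major components: registration of volunteers after CPR training", then installation and registration of public access defibrillators (PADs), then activation of the registered volunteers by dispatchers. The components are dated unevenly.

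- **Volunteer training and registration.** The paragraph on this component ends by placing the programme's start in "2013 as a pilot program and was implemented in 2014".
- **PAD installation.** The section says that "the Seoul health authority expanded the installation of PADs", with no date.
- **Dispatcher alert.** "In May 2015, Seoul launched the TM alert system".

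The Study design section uses one date for everything: "Since the intervention program started in May 2015, the period from January 2013 to December 2014 was defined as the pre-intervention period". It adds that "the period from January 2015 to December 2016 was defined as the post-intervention period", and describes the design in these terms: "This was a non-randomized, pre- and post-intervention trial".

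Under Data collection and variables, period (before or after) is the principal exposure. The outcome models under Statistical analysis adjust for season, day of week and time of day. They list no calendar-year or trend term. No section mentions the overlap, a wash-out or concurrent control districts.

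**The concern.** A before/after comparison needs a reference period that is clear of the thing being evaluated. Here the plan defines the intervention as a package, yet one named part of it was already under way during the years labelled pre-intervention. People who had taken the CPR course could act at an arrest without any text message, and bystander CPR is itself one of the listed outcomes. Registrations stay valid for two years, so anyone who registered during 2014 remained on the list into 2016. The volunteer pool therefore spans both periods.

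The primary endpoint, good neurological outcome at discharge, rests on the period contrast. If that odds ratio is reported as the effect of the programme, readers will take it as the package against nothing. A single binary period term cannot show the volunteer build-up, nor separate it from the switching-on of the alert.

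**Working it through.** The plan states no sample size, power, event count or effect size, so it has no figure to reproduce. The check is a comparison of dates, followed by an illustration of what can be said about direction.

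**Step 1. Months by component** (dates from Intervention program; periods from Study design)

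| Component | Stated start | Pre-period, Jan 2013–Dec 2014 (24 months) | Post-period, Jan 2015–Dec 2016 (24 months) |
|---|---|---|---|
| Volunteer training and registration | 2013 pilot, 2014 implementation, months not given | at most 24 of 24 counting the pilot; at most 12 of 24 counting 2014 only | 24 of 24 |
| PAD expansion | not dated | unknown | unknown |
| Text-message alert | May 2015 | 0 of 24 | 20 of 24 |

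The pre-period counts for volunteers are upper bounds. Only years are given, and enrolment would have accumulated.

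The months labelled post-intervention but before the alert are January–April 2015: 4/24 = 16.7%. If the launch fell at the end of May, this becomes 5/24 = 20.8%.

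**Step 2. Two readings of the 2013/2014 sentence**

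- If it dates the volunteer component only, which its position in that component's paragraph suggests, part of the package lies in the reference period.
- If it dates the whole programme, it contradicts the May 2015 start in Study design, and the cut between periods is itself in doubt.

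Either way the two sections must be reconciled.

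**Step 3. Can the direction of bias be settled?**

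Let the full package effect on the model scale be 1, and assume:

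- *f*: the share of that effect due to the volunteer component alone;
- *e*: the intensity of the 2013 pilot relative to 2014;
- *s*: the background trend per year, as a share of the full effect.

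Assume also that the volunteer component was at full strength from January 2014 and that the rest of the package began in May 2015. The period midpoints are two years apart, so

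contrast ÷ full effect = (4*f* + 20)/24 − *f*(12*e* + 12)/24 + 2*s*.

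None of *f*, *e* and *s* is in the documents. Values chosen only to test the sign:

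- *f* = 0, *s* = 0: 20/24 = 0.83. All of the shortfall comes from January–April 2015. With those months removed, the ratio is 1 and the reference period causes no attenuation.
- *f* = 0.25, *e* = 0.5, *s* = 0: 21/24 − 4.5/24 = 0.69.
- *f* = 0.5, *e* = 1, *s* = 0: 22/24 − 12/24 = 0.42.

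The trend that exactly offsets the shortfall is *s* = (1 − ratio)/2. This gives (1 − 0.83)/2 = 0.08, (1 − 0.69)/2 = 0.16 and (1 − 0.42)/2 = 0.29 of the full effect per year. A larger favourable trend makes the programme look better than it is. These figures show only that the sign is open; they do not estimate the size of the bias.

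**The case against.** The strongest reply is that the programme is, in substance, the alert. The Intervention program section opens by identifying it with the system launched in May 2015, and a sent message is a separate exposure in the analysis. A list of telephone numbers cannot bring a volunteer to an arrest until dispatchers send messages, so before May 2015 only a spill-over from a one-hour course could act. On that view earlier training is background care, not contamination. The documents also do not say how many volunteers were registered in 2013–2014, or whether the pilot covered the five study districts.

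Much of this stands. The early effect of the volunteer component may be close to nil, and no share can be assigned to it. But the plan itself lists three components and never states that the target is the alert alone. Even for the alert alone, growth in volunteer numbers and the undated PAD expansion are mixed with its introduction.

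A reader might infer that the programme's effect is understated, or biased toward no effect. The documents do not support that. Attenuation is expected only for the full package, only if training by itself improves response or outcome, and only if nothing else changed. In an uncontrolled comparison with no trend term, improving background care would push the other way. A reader might also infer that alerts were sent in 2014. The documents place the alert launch in May 2015.

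**Conclusion.** The inconsistency is real and affects what the main comparison can claim. Part of 2013 and 2014 is exposed to the first component, to an extent the documents do not quantify, and 4 of the 24 post-intervention months precede the alert. The before/after odds ratio does not estimate the three-component programme against no programme. The overlap may attenuate the package effect, but the net direction is uncertain.

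The conclusion rests on reading the 2013/2014 sentence as dating at least the volunteer component, and on the plan's own definition of the intervention. It does not depend on any assumed component share. 2013 cannot be treated as an unexposed year either, because the pilot falls in it.

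**What to change.** 1. Reconcile the Intervention program and Study design sections. Give a start date for each component, including PAD expansion, and the months of the 2013 pilot and 2014 implementation.
2. Keep the before/after contrast, but code January–April 2015 separately or exclude it from the post-intervention period.
3. Add a sensitivity model that replaces the binary period with four calendar levels: 2013, 2014, January–April 2015, and May 2015–December 2016. Report 2014 against 2013 only as a descriptive check. It mixes volunteer build-up with secular trend, and 2013 should not be described as unexposed.
4. Limit the conclusion to the change seen after the alert was added to a volunteer programme already running, together with any continued volunteer growth, PAD expansion and background trend. Do not present it as the effect of the full package.

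Arrest date is already collected, so the cost is one recode, one more model, slightly lower precision and a narrower claim. The calendar levels make the build-up visible but cannot separate it from background trend.

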### Study design

This was a non-randomized, pre- and post-intervention trial. Since the intervention program started in May 2015, the period from January 2013 to December 2014 was defined as the pre-intervention period, and the period from January 2015 to December 2016 was defined as the post-intervention period. The TM cases were defined as the cases for which an TM alert was sent. Other cases were defined as standard care cases (non-TM cases).

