#### Data collection and variables

We collected data from the Korean OHCA Registry including the ambulance run sheet, dispatch record, cardiac arrest in-depth registry, and medical records for outcomes from the Korea Centers for Disease Control and Prevention. We developed the TM alert system registry by linking the TM cases that had a message sent to the registered volunteers. We checked the OHCA registry to confirm whether or not the case was a real arrest. Such cases were excluded if they were not a cardiac arrest or death was confirmed at the scene and no transfer to the emergency department (ED) occurred.

The main exposure of interest was the intervention phase (before- and after-intervention periods), and the secondary exposure was TM sent from the TM alert system. Demographic factors that were collected included the following: date of arrest, time of the call (00:01-05:59, 06:00-11:59, 12:00-17:59, and 18:00-23:59), age, gender, and comorbidities (diabetes, hypertension, heart disease, and stroke). Community and EMS factors that were collected included the following: witness information, location of the arrest, bystander CPR, laypersons' use of a PAD, primary electrocardiogram (ECG) at the scene, EMS response time interval (RTI, from the time of the call to the time of EMS arrival at the scene), scene time interval (STI, from the time of arrival at the scene to the time of departure from the scene), transport time interval (TTI, from the time of departure from the scene to the time of EMS arrival at the hospital), prehospital airway management by an EMS provider (endotracheal intubation, supraglottic airway device, or bag valve mask). Hospital factors included the emergency department (ED) level (regional level 1 ED, local level 2 ED, local level 3 ED) and post-resuscitation care, such as percutaneous coronary intervention (PCI), targeted temperature management (TTM), and extracorporeal membrane oxygenation (ECMO).

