### Statistical analysis

The demographics of the registered volunteers, registered PADs, and the number of TM alerts sent during the study period were compared for the study setting. A descriptive analysis was performed to determine the distribution of the categorical variables (counts and proportions) and continuous variables (medians and inter-quartile ranges). The chi-square test was performed for categorical variables, and the Wilcoxon rank-sum test was performed to compare continuous variables across the intervention periods.

Adjusted odds ratios (ORs) with 95% confidence intervals (CIs) for bystander CPR and defibrillation by TM versus non-TM were calculated using multivariable logistic regression analysis with adjustment for potential confounders. Adjustment for age, gender, and comorbidities were included as confounders in Model 1, and time factors (season, weekend, and time of the arrest) and characteristics of the arrest (witnessed, location of arrest) in addition to the confounders in Model 1 were added in Model 2.

Multivariable logistic regression analyses for outcomes (good CPC, survival to discharge, and PROSC) were used. Model 1 was adjusted for demographic factors (age, gender, and comorbidities); Model 2 was adjusted for the demographic factors from Model 1 as well as time factors related to the event (season, weekday, and daytime), Utstein factors (initial ECG, witness, and place), and EMS factors (RTI, STI, TTI, and prehospital airway); Model 3 was adjusted for the same confounders as Models 1 and 2 as well as factors related to advanced hospital care (PCI, TTM, and ECMO).

For the sensitivity analysis, a final multivariable logistic regression analysis was conducted for the subgroup population when the call occurred during the study time (TM sent time), from 6 AM to 10 PM. The confounders were same as the main analyses for each outcome. The main exposure was TM (cases who received TM alerts) versus non-TM (cases who did not receive TM alerts) for bystander CPR and defibrillation during the before- and after-intervention periods for outcomes (PROSC, survival to discharge, and good CPC).

All the statistical analyses were conducted using SAS software, version 9.4 (SAS Institute Inc., Cary, NC, USA). P values were based on a two-sided significance level of 0.05.

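### The before-after odds ratio for good CPC, survival and prehospital ROSC cannot separate the programme from residual secular change, because no planned model has a trend, district or programme-district by period term

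*Combined protocol and SAP*

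**What the plan says.** Study design: "This was a non-randomized, pre- and post-intervention trial", with January 2013 to December 2014 as the pre period and January 2015 to December 2016 as the post period. Any case without an alert is a standard-care (non-TM) case.

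Data collection and variables: "The main exposure of interest was the intervention phase (before- and after-intervention periods"), while "the secondary exposure was TM sent from the TM alert system". Date of arrest is collected, and call time is banded: "time of the call (00:01-05:59, 06:00-11:59, 12:00-17:59, and 18:00-23:59").

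Statistical analysis: "Multivariable logistic regression analyses for outcomes (good CPC, survival to discharge, and PROSC) were used". That sentence gives outcomes but no exposure. The adjustment sets are:

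- Model 1: age, gender, comorbidities.
- Model 2: adds season, weekday, daytime; initial ECG, witness, place; response, scene and transport intervals; prehospital airway.
- Model 3: adds PCI, TTM, ECMO.

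The sensitivity analysis is "conducted for the subgroup population when the call occurred during the study time (TM sent time), from 6 AM to 10 PM", and "The confounders were same as the main analyses for each outcome". Its last sentence pairs TM versus non-TM with bystander CPR and defibrillation, and ends "during the before- and after-intervention periods for outcomes (PROSC, survival to discharge, and good CPC").

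Study setting and Intervention program: Seoul has 25 districts, about 10 million people and one dispatch centre. The alert was launched in May 2015 in 5 districts with 2.2 million people. Volunteer training is described as piloted in 2013 and implemented in 2014. The city expanded public defibrillators. Alerts were not sent at night. Study population refers to a study area in Seoul without saying whether that means 5 districts or 25.

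**The concern.** A before-after odds ratio measures everything that differed between the two periods after adjustment. If outcomes after cardiac arrest were improving or worsening for reasons outside the programme and outside the covariates, that change is added to the programme effect, and nothing in the planned models can take it out again.

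This affects the primary endpoint in both directions. A background improvement could produce a significant odds ratio with no programme effect, and a background deterioration could hide a real one. The setting may offer comparisons that would help (other districts, night hours, dated events), but none is planned.

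**Working it through.** **1. Which contrast is planned.** The main outcome sentence is silent. The declared design and main exposure are the period, and the sensitivity paragraph, although it seems to lack a conjunction, attaches the periods to the three clinical outcomes. The main-analysis text gives TM versus non-TM only for bystander CPR and defibrillation. A period contrast is therefore the best-supported reading, not a certain one.

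**2. Model terms against a multi-year trend.**

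| Term | Can it remove a trend? |
|---|---|
| Season, weekday, daytime | No; these repeat within each year, week or day |
| ECG, witness, place, EMS intervals, airway, PCI/TTM/ECMO | Only the part acting through them |
| Year or linear trend | Not in any model |
| District; programme district by period | Not in any model |
| 06:00-22:00 restriction | No; same period contrast, same covariates |

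If the study area were all 25 districts, the models would still lack a programme-district term.

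**3. Non-TM cases.** By definition they mix pre-period, night-time and daytime unalerted cases. Some are concurrent with alerted cases, but the plan does not use them to control the period odds ratio.

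**4. Size, illustrative.** The documents give no figure to reproduce. Assume no programme effect and a residual annual odds ratio b, with no absorption by covariates. The period midpoints are 2 years apart, so the spurious period odds ratio is b². The probability of two-sided p<0.05 uses the unpooled normal approximation, with assumed pre-period good-CPC rates of 3%, 5% and 10% and 500, 1,000 and 2,000 patients per period.

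| b | Upward: b² | P(p<0.05) | Downward: 1/b² | P(p<0.05) | Assumed true OR 1.3 under the downward trend: 1.3/b² |
|---|---|---|---|---|---|
| 1.05 | 1.10 | 6-16% | 0.91 | 6-15% | 1.18 |
| 1.10 | 1.21 | 8-47% | 0.83 | 8-41% | 1.07 |
| 1.15 | 1.32 | 13-80% | 0.76 | 11-71% | 0.98 |

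To the extent that covariates absorb the trend, the spurious ratios move toward 1 and the masked ones back toward 1.3.

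**5. Precision of analyses that could separate the two.**

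*Period by alert-hours.* With night share s and equal event rates by day and night, the SE relative to the in-hours contrast is √(1/s): 1.73 at s = 8/24 (arrests uniform over 24 hours) and 2.24 at s = 0.20 (assumed). With assumed rates of 6% by day and 3% by night, it is √[1 + ((1−s)/s)(0.06×0.94)/(0.03×0.97)]: 2.21 and 2.96.

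*Linear trend plus a step.* With uniform arrivals over 48 months, roughly constant information per month and a fraction q of time before the step, the SE multiplier is 1/√[1 − 3q(1−q)]: 2.00 at q = 24/48 and 1.92 at q = 28/48 (May 2015).

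*Programme district by post-launch.* The planned model's variance is v = 2/(n p(1−p)), with p and n as in step 4. Cases are taken as proportional to population (2.2 v 7.8 million), with equal rates and SD τ of district-level change. The variance is then k·v(1 + 2.2/7.8) + τ²(1/5 + 1/20), where k = 1 for 24/24 months and (1/28 + 1/20)/(2/24) = 1.029 for 28/20.

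- τ = 0: √1.282 = 1.13; √(1.029×1.282) = 1.15.
- τ = 0.3 (assumed): 1.20 (p = 3%, n = 500, 24/24) to 1.83 (p = 10%, n = 2,000, 28/20).
- A 4-df t reference (assumed): 2.776/1.960 = 1.42, a further 42% in interval width.

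**The case against.** The strongest reply is that the study openly calls itself a non-randomised before-after trial. Confounding by time is inherent in that design, and no visible text claims that the period odds ratio is causal. This stands as far as it goes: the design label is not an error. It does not answer the omission of feasible supplementary analyses bearing on what the primary-endpoint odds ratio can support.

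Second, the covariates may absorb much of any trend. They may; the amount is unknown. The illustration assumes none is absorbed, and its range of 6% to 80% is too wide to say how much this particular study is affected.

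Third, unalerted patients exist after launch, so it would be wrong to say that there is no concurrent group at all. The correct statement is narrower: that group is not used for the period contrast and, as defined, would be a poor control for it.

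Fourth, a reader might infer from the mention of the 2010 and 2015 guidelines that a protocol change fell inside the window and confounds the result. The documents give no local adoption date, so this is a reason to look, not evidence of a shift.

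**Conclusion.** The point holds in limited form and should be acted on. On the best-supported reading, the period odds ratios for good CPC, survival and prehospital ROSC combine the programme with residual secular change, and no planned analysis of those outcomes separates them. An assumed residual annual odds ratio of 1.05 to 1.15 would by itself give a period odds ratio of 1.10 to 1.32; the reverse trend would reduce an assumed true 1.3 to between 1.18 and 0.98.

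A reader might go further and infer that a trend existed, that the result is biased, or that a significant odds ratio would be false. The documents support none of these: they give no trend, event rates or patient numbers, and the direction of any drift is unknown. The conclusion rests on the missing model terms and on the exposure reading, which the sponsor should confirm.

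**What to change.** State the exposure in the main outcome models and define the study area. Keep the before-after odds ratio, but do not attribute it to the programme on its own. Add the following as supplementary analyses.

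**(a) With data already held.** Fit period by alert-hours (06:00-21:59 v 22:00-05:59) in the programme districts. Use exact call time, because the 18:00-23:59 band straddles 22:00; the planned 6 AM to 10 PM subgroup implies that exact time is available. State that this contrast targets the alert only, since training and defibrillators are not restricted by hour, and that bystander presence and defibrillator access may also differ at night. The cost is an SE about 1.7-2.2 times that of the in-hours contrast, or 2.2-3.0 times if the night event rate is half. A calendar-trend or interrupted-series model using date of arrest also needs no new data. It roughly doubles the SE and depends on the assumed shape of the trend.

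**(b) With a wider registry extract.** First verify that the registry covers the other 20 districts and that they had no alert or comparable volunteer roll-out to December 2016; exclude any that did. Then fit district and calendar-quarter effects with a programme-district by post-launch term (from May 2015). Use a small-cluster correction or permutation of the 5-of-25 assignment (53,130 sets), noting that permutation assumes exchangeable districts and that the 5 are not described as randomly chosen. State the parallel-trends assumption, and that the 2013 pilot and 2014 implementation mean the pre-launch months may already be exposed. Because the defibrillator expansion was city-led, say that the contrast mainly estimates the alert.

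The SE for (b) is 13-15% above the planned model's with no district heterogeneity and 20-83% above it at τ = 0.3, plus small-cluster widening of about 42% with a 4-df reference. Part of the larger figure arises because the planned SE ignores between-district variation. If exclusions halved the control population to 3.9 million (assumed), the penalty at τ = 0 and 24/24 months would be √(1 + 2.2/3.9) = 1.25.

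### The post-intervention period opens in January 2015, four months before the May 2015 launch of the dispatcher alert, so at least 4 of its 24 months are misclassified in every before-after comparison

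*Combined protocol and SAP*

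**What the plan says.** The Intervention program section gives the launch date: "In May 2015, Seoul launched the TM alert system". The Study design section repeats it ("Since the intervention program started in May 2015") and offers it as the reason for the period split. The same sentence then sets January 2013-December 2014 as the pre-intervention period and continues: "the period from January 2015 to December 2016 was defined as the post-intervention period". It gives no reason for January.

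The Data collection and variables section makes this split the principal exposure: "The main exposure of interest was the intervention phase (before- and after-intervention periods". The Study population section enrols continuously from January 2013 to December 2016, with no transition or washout period. The one sensitivity analysis restricts by hour of call, 6 AM to 10 PM, and keeps the same two periods for the clinical outcomes.

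The timing of the other two components is less clear. At the end of the volunteer-network paragraph, the programme is said to have started in "2013 as a pilot program and was implemented in 2014". It is not clear whether this means volunteer training and registration or the whole programme. The defibrillator component has no date: "Second, the Seoul health authority expanded the installation of PADs".

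**The concern.** The reason given for the split contradicts the boundary it is meant to support. Patients who arrested in January-April 2015 could not have had an alert sent, but they are analysed as post-intervention.

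This affects the period comparison of good CPC, survival to discharge and prehospital ROSC in Models 1-3, the same three outcomes in the 6 AM-10 PM analysis, and the chi-square and Wilcoxon tests across periods. It does not affect the models for bystander CPR and defibrillation, whose exposure is whether an alert was sent: "The main exposure was TM (cases who received TM alerts) versus non-TM (cases who did not receive TM alerts) for bystander CPR and defibrillation".

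Two things are at stake. First, the headline odds ratio cannot be described as before versus after launch. Second, the alert's contribution to the contrast is diluted. The plan's covariates do not help: Models 2 and 3 include "time factors related to the event (season, weekday, and daytime", but no term for calendar trend. If the 2013/2014 sentence refers to volunteer training and registration, the pre period already contains part of the intervention, and the contrast is not all three components against none.

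**Working it through.** The plan gives no sample size, event rate or power, so there is no design figure to reproduce. The dates come from the documents. Baseline risks, odds ratios, case numbers and trends are assumptions.

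**Misclassified time.** The post period, January 2015-December 2016, is 24 months or 731 days. The day of launch in May is not stated.
- Launch on 1 May: 4/24 months = 16.7% (120/731 days = 16.4%).
- Launch on 31 May: 150/731 days = 20.5%.

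Four months is therefore the minimum.

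**Dilution.** Assume even case flow, no trend and no alert effect before launch. Let p0 be the baseline risk and p1 the risk with the alert. The post-period risk is then (20·p1 + 4·p0)/24, so the risk difference shrinks to 20/24 = 83% of its true value.

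Example with p0 = 5% and OR 1.5: baseline odds are 0.05/0.95 = 0.0526. Multiplied by 1.5 they are 0.0789, so p1 = 7.32%. The diluted risk is (20 × 7.32% + 4 × 5%)/24 = 6.93%, and the resulting OR is (0.0693/0.9307)/0.0526 = 1.41.

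Over p0 = 3%, 5% and 8%:

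| True OR | Estimated, launch 1 May | Estimated, launch 31 May |
|---|---|---|
| 1.3 | 1.25 | 1.24 |
| 1.5 | 1.41-1.42 | 1.39-1.40 |
| 2.0 | 1.82-1.83 | 1.78-1.79 |

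**Cost in sample size.** Take z = risk difference / unpooled binomial standard error. The inflation factor is (z with all 24 post months exposed / z as written)². It is 1.37-1.42 over the same baselines and ORs, close to the rough value (24/20)² = 1.44.

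**Illustration.** Assume 2,000 cases per 24 months, p0 = 5%, OR 1.5 and a two-sided 0.05 test:

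| Windows | z relative to plan | z ratio squared | Power |
|---|---|---|---|
| As written, 24 v 24 months | 1 | 1 | 73% |
| January-April 2015 excluded, 24 v 20 | 1.12 | 1.25 | 82% |
| Matched, 20 v 20 | 1.08 | 1.17 | 80% |

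Power as written falls to about 70% (0.695) if launch was on 31 May.

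**Secular trend.** Let the monthly odds change by a constant yearly factor, and apply the alert OR from month 29 (May 2015). A rise in the odds of good CPC of about 3% a year (true OR 1.5) or 4.5% a year (true OR 2.0) would exactly cancel the dilution. With a 5% yearly rise and true OR 1.5, the plan's split gives 1.56 and matched windows give 1.65.

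**Gap between period midpoints.**
- As written: January 2014 to January 2016, 24 months.
- Only the four post months dropped: January 2014 to March 2016, 26 months, with seasons unbalanced.
- Matched May-December windows: March 2014 to March 2016, 24 months, with seasons balanced.

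**The case against.** The date mismatch is not in dispute. The best counter-arguments concern the remedy and the size.

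- **The new window may lie further from the truth.** If outcomes were improving anyway, dilution partly offsets the trend. At a 5% baseline, the matched windows miss the true OR by more than the plan's split once the yearly rise in odds exceeds about 1.4% (true OR 1.5) or 2.2% (true OR 2.0). This is correct, and it shows that fixing dates does not fix an uncontrolled before-after design. But an accidental offset by an unmodelled trend is no reason to misclassify exposure.
- **Matching has a cost.** Dropping January-April 2013 raises the share of the pre period that falls in 2014 from 12/24 (50%) to 12/20 (60%). If volunteer registration was implemented in 2014, the pre period is somewhat more contaminated. This stands, but it is minor and depends on one reading of an ambiguous sentence.
- **The dilution figures treat the alert as the whole effect.** If half the effect on the risk-difference scale came from components already active before launch, a true OR of 1.5 (5% baseline) would be estimated as about 1.46. This stands: 1.42 is towards the pessimistic end for the programme as a whole, though not for the alert alone.
- **Changing the window afterwards invites suspicion,** particularly as the new window gave the larger OR in the scenarios calculated. This stands, and is why the change must be disclosed and both results shown.
- **Reconciliation should come first.** If the 2013/2014 sentence means the whole programme, May 2015 may not be the right boundary. That is a fair point about order. On no reading, however, do the documents support January 2015.

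**Conclusion.** The concern holds. At least 4 of 24 post months (16.7%, up to 20.5% of days) precede the alert in every period comparison, including that of the primary endpoint. This needs no assumption beyond the stated launch month.

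The effect on the estimate is conditional. Without a secular trend, and with no alert effect before launch, the bias is toward the null and moderate: about 1.5 to 1.42, or 2.0 to 1.83. With a trend, the net direction in the reported OR is not known. Because the defect lies in the definition of the main exposure, it should be corrected before the before-after result is interpreted.

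**What to change.** 1. State what began in 2013, what was implemented in 2014 and what started in May 2015, including when defibrillator expansion took place. Reconcile the Intervention program and Study design sections on this before fixing the boundary.
2. Unless that reconciliation moves the start date, define post-intervention as launch to December 2016, exclude January-April 2015, and use May 2013-December 2014 as the pre period. Give the exact launch day; if it was after 1 May, move both window starts to match. Matched windows keep seasons balanced in the descriptive tests and Model 1, which have no season term.
3. Report the January 2015 split as a sensitivity analysis, and say that the main window was changed after the periods were first defined.
4. If the 2013/2014 sentence refers to volunteer training and registration, state that the contrast estimates the addition of the dispatcher alert, with any concurrent growth in volunteers and defibrillators, and not the full programme against none.
5. State that the new dates correct the exposure definition only and leave secular trend unaddressed.

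The cost is a date cut-off on arrest dates already collected and a few sentences of text. Eight of 48 months, about one sixth of cases under even flow, leave the main analysis. In the illustration above, power still rises from 73% to 80%.
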